| Key Eligibility Criteria: | Subject must be ≥ 18 years old, have newly diagnosed AML with intermediate or poor risk cytogenetics, have confirmed CR or CRi following completion of intensive Induction and Consolidation chemotherapies, have achieved first CR or CRi (after induction) within 120 days of the first dose of study drug or be no more than 75 days since last dose of intensive conventional (including both Induction and Consolidation) chemotherapies until enrollment, and have an Eastern Cooperative Oncology Group (ECOG) performance status of ≤ 2. The key laboratory requirements are as follows: • creatinine clearance ≥ 30 mL/minute; calculated by the Cockcroft Gault formula or measured by 24-hour urine collection; • bilirubin < 3.0 × upper limit of normal (ULN) (adequate liver function) for Part 1, or bilirubin < 2.0 × ULN for Part 3; • absolute neutrophil count ≥ 1,500/μL; • platelets ≥ 100,000/μL. |
| Study Drug and Duration of Treatment: | Part 1: Venetoclax QD for each 28-day cycle for 24 cycles + AZA QD for 5 days (Days 1 to 5) of each 28-day cycle up to 6 cycles. At investigator's discretion, subjects benefiting from treatment at the end of Cycle 24 may continue on venetoclax for up to 48 cycles. Part 3 (Dose Finding): Venetoclax QD for each 28-day cycle up to 24 cycles + oral AZA QD for 14 days (Days 1 to 14) of each 28-day cycle up to 24 cycles. |
| Date of Protocol Synopsis: | 26 April 2024 |

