2.3 Treatment Assignment and Blinding

This study has two parts:

- Part 1 Dose Confirmation (see protocol V2.0 Section 4.1)
- Part 2 randomized, open label, 2-arm

In Part 2 of the study, subjects will be randomized 1:1 to one of the following two arms:

- Arm A: Receive combination of Venetoclax and AZA for up to the first 6 cycles and Venetoclax (monotherapy) from Cycle 7 to Cycle 24.
- Arm B: Receive best supportive care (BSC) only.

Randomization will be stratified by:

[figure not shown]

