9.2 Treatment-Emergent Adverse Events

Treatment-emergent AEs are defined as any AE with the onset that is on or after the first dose of study drug until 30 days after the last dose of the study drug for subjects in Part 1 and ARM A of Part 2. If an incomplete or missing onset date was collected for an AE, the AE will be assumed to be treatment-emergent unless there is evidence that confirms that

[figure not shown]
the AE was not treatment-emergent (e.g., the AE end date was prior to the date of the first dose of study drug). For subjects randomized to Arm B, AEs with an onset date on or after the date of randomization up to 30 days after the end of Cycle 24, disease relapse or study discontinuation, whichever is the earliest will be included in the summaries of treatment-emergent AEs.

All treatment-emergent AEs will be summarized overall, for venetocalx combination with azacitidine as well as for venetoclax monotherapy separately.

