9.2.1 Adverse Event Overview

An overview of AEs will be presented consisting of the number and percentage of subjects experiencing at least one event for each of the following AE categories:

- Any treatment-emergent AE
- Any treatment-emergent AE with NCI toxicity (CTCAE V5.0) grade ≥ 3
- Any treatment-emergent AE with NCI toxicity (CTCAE V5.0) grade 3 or 4
- Any treatment-emergent AE with reasonable possibility related to venetoclax as assessed by the investigator (for Arm A and Part 1)
- Any treatment-emergent AE with reasonable possibility related to azacitidine as assessed by the investigator (for Arm A and Part 1)
- Any treatment-emergent serious AE
- Any treatment-emergent AE leading to discontinuation of venetoclax (for Arm A and Part 1)
- Any treatment-emergent AE leading to dose interruption of venetoclax (for Arm A and Part 1)
- Any treatment-emergent AE leading to dose reduction of venetoclax (for Arm A and Part 1)
- Any treatment-emergent AE leading to discontinuation of azacitidine (for Arm A and Part 1)
- Any treatment-emergent AE leading to dose interruption of azacitidine (for Arm A and Part 1)

- Any treatment-emergent AE leading to dose reduction of azacitidine (for Arm A and Part 1)
- Any treatment-emergent AE leading to death
- All deaths

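### Part 1 adverse events are split by treatment phase as crude percentages over windows of about 168 and 534 days, with no person-time and no stated phase window or denominator

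*SAP*

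**What the plan says.** For Part 1, SAP 9.2 treats an AE as treatment-emergent if its onset falls "on or after the first dose of study drug until 30 days after the last dose of the study drug". For Arm B of Part 2, which the protocol has since removed, the window instead runs from randomization "up to 30 days after the end of Cycle 24, disease relapse or study discontinuation, whichever is the earliest". SAP 9.2 then adds: "All treatment-emergent AEs will be summarized overall, for venetocalx combination with azacitidine as well as for venetoclax monotherapy separately". That sentence names no measure. The measure comes from SAP 9.2.1, which reports the "number and percentage of subjects experiencing at least one event for each of the following AE categories"; SAP 9.1 and 9.2.2 count each subject once per event. Protocol 7.4 also works in percentages of subjects.

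SAP 2.3 describes the two phases for Arm A: "Receive combination of Venetoclax and AZA for up to the first 6 cycles and Venetoclax (monotherapy) from Cycle 7 to Cycle 24". The Protocol synopsis and section 4.1 give Part 1 the same pattern, with AZA for up to 6 cycles and venetoclax for 24. Subjects still benefiting at the end of Cycle 24 "may continue on venetoclax for up to 48 cycles". The SAP is written to protocol version 2.0 and mentions no treatment beyond Cycle 24.

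Neither document says when one phase ends and the next begins, who forms the denominator of each phase, or which phase owns an event near the switch. SAP 9.1 limits safety analyses to the Safety Analysis Set, and SAP 4.0 defines no phase-specific set. SAP 6.0 summarizes drug exposure but does not link it to AE counts. Neither document plans an exposure-adjusted rate or a time to first AE.

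**The concern.** The chance of recording at least one event grows with the time a subject is watched. Two phases with the same event rate but very different lengths will therefore usually show different percentages. The natural use of the phase split is to see whether toxicity changes once AZA stops. A reader could take a higher monotherapy percentage as worse tolerability when it reflects only longer observation. If the denominator includes subjects who never reached monotherapy, the error can run the other way and make that phase look milder than it is. Part 1 has 66 enrolled subjects and is still in the current protocol, so these tables may actually be produced.

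**Working it through.** The plan gives no phase figure to reproduce. Protocol Tables 9 and 10 rest on similar at-least-one-event logic and do reproduce, for example 1 − 0.95^20 = 0.64 and 1 − 0.95^24 = 0.71.

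**Planned windows** (28-day cycles, all planned cycles completed, boundary taken at the end of Cycle 6)
- Combination: 6 × 28 = 168 days.
- Monotherapy to Cycle 24: 18 × 28 + 30 = 534 days; 534/168 = 3.2.
- Monotherapy to Cycle 48: 42 × 28 + 30 = 1206 days; 1206/168 = 7.2.

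**Equal rate, no dropout.** With a constant rate λ per year and a window of T days, the crude percentage is 1 − exp(−λT/365.25). The documents give no AE rate, so λ is an assumption shown over a range.

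| λ per year | Combination | Monotherapy to C24 | Monotherapy to C48 |
|---|---|---|---|
| 0.1 | 4.5% | 13.6% | 28.1% |
| 0.25 | 10.9% | 30.6% | 56.2% |
| 0.5 | 20.5% | 51.9% | 80.8% |
| 1.0 | 36.9% | 76.8% | 96.3% |

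**Equal rate, with dropout.** Take λ = 0.5 per year and an assumed constant hazard h of stopping all treatment (1 month = 30.4375 days; λ and h converted to per day). Subjects who stop keep a 30-day tail; those who switch leave the combination window at day 168.
- Combination: 1 − [h/(h+λ) × (1 − e^(−168(h+λ))) × e^(−30λ) + e^(−168(h+λ))].
- Monotherapy, entrants only: 1 − e^(−30λ) × [h/(h+λ) × (1 − e^(−504(h+λ))) + e^(−504(h+λ))].
- Share reaching monotherapy: e^(−168h).
- Monotherapy over all treated: entrants' percentage × share reaching.

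| h per month | Combination | Share reaching | Monotherapy, entrants | Monotherapy, all treated |
|---|---|---|---|---|
| 2% | 19.9% | 89.5% | 45.5% | 40.8% |
| 6% | 18.6% | 71.8% | 36.1% | 25.9% |
| 10% | 17.5% | 57.6% | 29.5% | 17.0% |

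The true rate is the same in every cell. Depending on dropout and on an unstated denominator, monotherapy looks more than twice as toxic as the combination, or about equal to it.

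**After the fix.** Subjects with a first event divided by patient-time at risk returns the common rate in both phases: 0.5/12 × 100 = 4.2 per 100 patient-months.

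**The case against.** Several objections have force.

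- **No decision depends on it.** The Part 1 objective is the RPTD and its endpoint is DLTs, assessed in Cycle 1 (Protocol 3, 3.1, 4.1 and 6.3). Neither document says that the phase split is meant to test the effect of stopping AZA, and no AE test is planned. This stands, and it limits the weight of the point.
- **Exposure is reported.** SAP 6.0 gives duration and number of cycles for both drugs, so a reader can see that the phases differ in length. That is a warning, but it does not let the reader correct a percentage.
- **The denominator is not shown to be wrong.** A reader might infer that the monotherapy percentages will be taken over the full Safety Analysis Set. SAP 9.1 says who may enter safety analyses; it does not require non-entrants in the monotherapy denominator. The documents support only that the denominator is undefined.
- **Person-time has its own assumption.** If first events cluster early in a phase, dividing by a long monotherapy time can make that phase look safer. This stands and belongs in the table notes.
- **The BSC arm.** A reader might infer a biased safety comparison between arms, because the Arm A window closes after the last dose while the Arm B window does not depend on stopping a drug. The texts do differ, and the SAP lists safety against BSC as an objective. But the protocol removed Part 2 from Version 5.0, and its current objectives contain no BSC comparison. Nor would the direction be known. With an assumed BSC median RFS of 12 months, an assumed RFS hazard ratio of 0.65 (the plan's value is redacted) and 0.5 events per year in both arms, Arm A against Arm B is 45.7% against 39.8% with no stopping of drug before relapse. It is 40.2% against 39.8% at 20% stopping per year, and 31.8% against 39.8% at 50%.

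**Conclusion.** The point holds for the Part 1 phase tables, as a modest improvement to safety reporting. The planned windows differ 3.2-fold to Cycle 24 and 7.2-fold to Cycle 48. With equal event rates and no dropout, the monotherapy percentage is about two to three times the combination percentage to Cycle 24 over the assumed range of 0.1 to 1.0 per year. Dropout narrows the gap, and a denominator of all treated subjects can close it. These sizes rest on assumed constant event and stopping rates and on a phase boundary at the end of Cycle 6, none of which the documents give. What does not depend on those values is that the tables as planned cannot separate a change in toxicity from a difference in observation time or denominator.

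The point does not extend to the RPTD or to the removed comparison with BSC. Nor does it reach Part 3, where both drugs may run for up to 24 cycles and no monotherapy phase is planned.

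**What to change.** For Part 1 only:

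1. Beside the crude percentages, give exposure-adjusted incidence by phase for the SAP 9.2.1 overview categories: subjects with a first event in the phase per 100 patient-months at risk in that phase.
2. Use subjects with at least one venetoclax dose after the last AZA dose as the monotherapy denominator, and show the number.
3. State the phase boundary and which phase owns events near the switch. This has to be settled together with item 2. AZA is given on Days 1 to 5 and venetoclax continues in the same cycle, so counting literally from the last AZA dose would admit almost every subject, including those who stopped everything in mid-cycle. Starting monotherapy at Day 1 of the first cycle given without AZA would match the Cycle 7 start in SAP 2.3.
4. Let the definitions cover treatment to Cycle 48.

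The cost is a few extra tables from dosing and AE dates already collected. The rate assumes a roughly constant hazard within each phase, so early clustering should be noted. It also does not remove selection: those who enter monotherapy are the subjects who stayed on treatment, so the phase contrast remains descriptive. No table with a common window across arms is needed, and the Arm B text can be dropped or marked not applicable when the SAP is aligned to the current protocol.

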9.2.1 Adverse Event Overview

An overview of AEs will be presented consisting of the number and percentage of subjects experiencing at least one event for each of the following AE categories:

- Any treatment-emergent AE
- Any treatment-emergent AE with NCI toxicity (CTCAE V5.0) grade ≥ 3
- Any treatment-emergent AE with NCI toxicity (CTCAE V5.0) grade 3 or 4
- Any treatment-emergent AE with reasonable possibility related to venetoclax as assessed by the investigator (for Arm A and Part 1)
- Any treatment-emergent AE with reasonable possibility related to azacitidine as assessed by the investigator (for Arm A and Part 1)
- Any treatment-emergent serious AE
- Any treatment-emergent AE leading to discontinuation of venetoclax (for Arm A and Part 1)
- Any treatment-emergent AE leading to dose interruption of venetoclax (for Arm A and Part 1)
- Any treatment-emergent AE leading to dose reduction of venetoclax (for Arm A and Part 1)
- Any treatment-emergent AE leading to discontinuation of azacitidine (for Arm A and Part 1)
- Any treatment-emergent AE leading to dose interruption of azacitidine (for Arm A and Part 1)

- Any treatment-emergent AE leading to dose reduction of azacitidine (for Arm A and Part 1)
- Any treatment-emergent AE leading to death
- All deaths

9.2.2 Treatment-Emergent Adverse Events by SOC and/or PT

Treatment-emergent adverse events will be summarized by SOC and PT. Specific adverse events will be counted once for each subject for calculating percentages, unless stated otherwise. In addition, if the same adverse event occurs multiple times within a subject, the highest severity and level of relationship to investigational product will be reported. Treatment-emergent adverse events will be summarized by PT and sorted by decreasing frequency for the total active group.

9.2.3 SAEs and Deaths

SAEs (including deaths) will be summarized by SOC and PT and in listing format.

The number of subject deaths and causes of death will be summarized

- (1) all deaths from all causes.
- (2) deaths occurring within 30 days of the first dose of study drug (Arm A or Part 1).
- (3) deaths occurring within 30 days of the last dose of study drug (Arm A or Part 1).
- (4) deaths occurring within 30 days of the randomization (Arm B).
- (5) deaths occurring within 30 days of the end of Cycle 24, disease relapse or study discontinuation, whichever is the earliest (Arm B).

9.2.4 Adverse Events of Special Interest

Adverse events of special interest (AESI) will be summarized by SOC and PT and will be based on standardized or company MedDRA queries (SMQs or CMQs). AESI is Tumor Lysis Syndrome (TLS) and will be identified using the following search criteria:

Table 2. AESI Search Criteria

[figure not shown]
Area of Safety Interest	Search Criteria	
Tumor Lysis Syndrome (AE)	SMQ – "Tumor Lysis Syndrome" (narrow)	

Number and percent of subjects experienced treatment-emergent TLS occurring within 7 days from first dose for Arm A (or randomized date for Arm B) will be summarized.

In addition, treatment-emergent AEs and serious AEs for the following selected grouped preferred terms (PTs) including, but not limited to, those listed in Table 3, will be summarized.

Table 3. Selected Adverse Events

Selected Adverse Events	Search Criteria	
grade ≥ 3 Neutropenia	PT terms – "neutropenia," "neutrophil count decreased," "febrile neutropenia," "agranulocytosis," "neutropenic infection," and "neutropenic sepsis"	
grade \geq 3 Infection, including opportunistic infection	SOC of "infections and infestations"	
Haemorrhages	SMQ – "Haemorrhages" (narrow)	
Anaemia	PT terms - "Anaemia" and "Haemoglobin decreased"	
Thrombocytopenia	PT terms - "Thrombocytopenia" and "Platelet count decreased"	
Leukopenia Neutropenia and neutrophil count decrease	PT terms – "Leukopenia" and "White blood cell count decreased" PT teams - "neutropenia" and "neutrophil count decreased"	

[figure not shown]
9.3 Analysis of Laboratory Data

Unless otherwise specified, analysis of laboratory data will include post-baseline measurements within 30 days of the last dose of the study drug for Arm A or Part 1 or within 30 days of the end of Cycle 24, disease relapse, or study discontinuation whichever is the earliest for subjects in Arm B.

Data collected from central and local laboratories, including additional laboratory testing due to an SAE, will be used in all analyses. The clinical laboratory tests defined in the protocol operations manual (e.g., hematology and clinical chemistry) will be summarized. Change from baseline will be summarized and presented for each lab test at scheduled post-baseline visits defined in Appendix C. Baseline is defined as the last non-missing observation before the first administration of study drug or randomization if no study drug is given.

For shifts relative to National Cancer Institute Common Toxicity Criteria for Adverse Events (NCI CTCAE version 4.03), baseline and post-baseline laboratory observations will be categorized as grade 0, grade 1, grade 2, grade 3, or grade 4 according to NCI CTCAE grade version 4.03. The baseline grade is defined as the grade of the last measurement collected on or prior to the first dose of study drug (or randomization for non-treated subjects). In cases where multiple values are collected on the same day, the maximum grade value will be selected as the value for that day. The maximum NCI toxicity grade value is the value with highest NCI toxicity grade collected after the first dose of study drug.

For each lab test, cross tabulate will be generated for the number of subjects with baseline values of grade 0, grade 1, grade 2, grade 3, grade 4, or missing grade versus maximum post-baseline values of grade 0, grade 1, grade 2, grade 3, grade 4, or missing grade. All subjects in the safety analysis set will be included in the cross tabulation regardless whether baseline or post-baseline measurements are collected.

The separate laboratory shifts tables based on the two criteria below will be generated for each laboratory tests related to CTCAE:

- 1. Shifts from grade 0 (normal) at baseline to grade 1 4 post-baseline (maximum) and worsening from an abnormal baseline value of at least one grade up post-baseline (maximum)
- 2. Shifts from grade 0 2 at baseline to grade 3 or 4 post-baseline (maximum) and from grade 3 at baseline value to grade 4 post-baseline (maximum).

For above shift tables, baseline grade of 0 (normal) will be imputed for all subjects with at least one post-baseline but missing a baseline value for each lab test.

[figure not shown]
Detailed listings of all data for subjects experiencing NCI CTCAE grade 3 to 4 blood chemistry and hematology values will be provided.

DILI will be assessed using laboratory data, including alanine aminotransferase (ALT), aspartate aminotransferase (AST) and total bilirubin (TBILI), based on Hy's law criteria. Number and percentage of subjects with liver enzyme value meeting the Hy's law criteria for potential drug-induced liver injury (ALT $> 3 \times$ ULN or AST $> 3 \times$ ULN and TBILI $> 2 \times$ ULN within 72 hours of each other) will be presented.

9.4 Safety Subgroup Analyses

Safety analyses described in Section 9.2 (adverse events) may be summarized for the subgroups including, but not limited to, those defined below:

- Age $(< 60, \ge 60)$
- Gender (Male, Female)
- region (
 , or other regions requested by regulatory agencies)
- Hepatic impairment at baseline (Yes, No)

• Renal impairment at baseline (Yes, No)

Definition of hepatic impairment at baseline and renal impairment at baseline are described in Appendix F.

10.0 Interim Analyses

Interim review of safety data from Part 2 of the study will be conducted at the following time points:

- The first analysis to review the safety data will occur when 20 subjects have been on study for 3 cycles in Part 2 of the study
- The subsequent reviews of safety data will occur approximately every 6 months after the first review of safety data.

Two planned interim analysis (IAs), one for futility and one for efficacy, for the RFS endpoint will be conducted:

[figure not shown]
- RFS Futility IA (IA1) at 40% RFS (
- RFS Efficacy IA (IA2) at 75% RFS (

The Lan-DeMets error spending function with O'Brien-Fleming boundary will be used to determine the futility and efficacy stopping boundaries for the RFS endpoint (Table 4).

Table 4. Stopping Boundaries for IAs and FA of RFS

Analysis Time	Number of RFS Events	Efficacy Stopping Boundaries (One-sided P-value/ Observed HR)	Futility Stopping Boundaries (One-sided P-value/ Observed HR)
RFS IA1		NA	≥ 0.621/≥ 1.066
RFS IA2		$\leq 0.010 / \leq 0.703$	NA
RFS FA		≤ 0.022/≤ 0.770	NA

IA = interim analysis; FA = final analysis; HR = hazard ratio; RFS = relapse-free survival; NA = not applicable

10.1 Data Monitoring Committee

The interim analyses will be performed by an independent Statistical Data Analysis Center. An Independent Data Monitoring Committee (IDMC) composed of persons independent of AbbVie and with relevant expertise in their field will review the above interim analyses.

A separate IDMC Charter will be prepared outside of the protocol and will describe the roles and responsibilities of the IDMC members, frequency of data reviews, and relevant safety data to be assessed.

The IDMC will make a recommendation based on RFS and OS to either to stop for success or futility at each interim analysis or continue the study as planned. The planned stopping boundaries are described in Table 4 for RFS. The actual stopping boundaries at IA2 and FA of RFS will be derived using Lan-DeMets alpha spending function based on the observed number of RFS events in the extracted database. The actual stopping boundaries will be presented in the IDMC charter addendum. At RFS IA2, if the IDMC informs the Sponsor that the RFS data is statistically significant and in favor of the venetoclax arm, upon notification from the Sponsor's Internal Executive Review Committee and after consultation with regulatory authorities as required to ensure maturity of data for registration, the Sponsor will then prepare regulatory submissions globally based on the available data while the study will continue for 100% OS evaluation. If the results of the RFS analysis are not statistically significant in favor of the venetoclax arm, the study will continue to follow protocol-specified procedures until the final analysis.

Details of the IDMC review will be presented in the IDMC Charter.

11.0 Overall Type-I Error Control

The fixed sequence testing procedure will be performed with a significance level of 0.025 (one-sided) for the primary efficacy endpoint and key secondary efficacy endpoints sequentially. The ranking and alpha spending of the key secondary efficacy endpoints are described in Table 5. If the statistical test is not significant for the primary efficacy endpoint, then statistical significance will not to be declared for any of the key secondary endpoints. The Lan-DeMets alpha spending function with O'Brien Fleming boundary will be used at the efficacy interim analysis to ensure that the false positive rate for RFS is controlled at the one-sided 0.025 level.

[figure not shown]

Table 5. Testing Sequence and Alpha-Spending Boundaries (One-Sided P value) for the Primary and Key Secondary Endpoints

Testing		Timing of Analysis			
Sequence	Endpoint	RFS IA1	RFS IA2	RFS FA	OS FA
1	RFS	0.0001	As specified in Table 4	As specified in Table 4	NA
2	OS	0.0001	0.0001	OBF ^b	OBF^b
3	Time to deterioration in QoL ^a	0.0001	0.025	NA	
4	PROMIS Cancer Fatigue SF 7a ^a	NA	0.025	NA	
5	MRDa	NA	0.025	NA	

RFS = relapse-free survival; FA = final analysis; HR = hazard ratio; IA = interim analysis; NA = not applicable; OS = overall survival

- a. Will be tested one time using the data at 75% RFS interim (IA2).
- b. OBF (O'Brien-Fleming boundary) will be calculated based on (100% information).

[figure not shown]
